# APPENDIX F: 2018 AMERICAN HEART ASSOCIATION/AMERICAN COLLEGE OF CARDIOLOGY GUIDELINE ON THE MANAGEMENT OF BLOOD CHOLESTEROL

The manuscript (to appear in the Journal of the American College of Cardiology [ACC]) of the 2018 American Heart Association (AHA)/ACC Guideline on the Management of Blood Cholesterol can be accessed at the following link:

https://www.ahajournals.org/doi/10.1161/cir.00000000000000625

The "Guidelines Made Simple" version of the 2018 AHA/ACC Guideline on the Management of Blood Cholesterol, which contains excerpts from the full guideline, can be accessed at the following link:

https://www.acc.org/~/media/Non-Clinical/Files-PDFs-Excel-MS-Word-etc/Guidelines/2018/old Guidelines-Made-Simple-Tool-2018-Cholesterol.pdf

<sup>1 Grundy SM, Stone NJ, Bailey AL, et al. 2018 AHA/ACC/AACVPR/AAPA/ABC/ACPM/ADA/AGS/APhA/ASPC/NLA/PCNA Guideline on the Management of Blood Cholesterol: A Report of the American College of Cardiology/American Heart Association Task Force on Clinical Practice Guidelines. *J Am Coll of Cardiol*. 2018. Nov 8. pii: S0735-1097(18)39034-X. doi: 10.1016/j.jacc.2018.11.003. [Epub ahead of print].

# APPENDIX G: CORONAVIRUS DISEASE 2019 CONTINGENCY MEASURES

The following contingency measures have been established to mitigate the potential impact that Coronavirus Disease 2019 (COVID-19) has on study conduct, patient safety, and data integrity. It is important to note that these mitigations are specific to situations where COVID-19 is impacting study conduct. In the absence of a COVID-19 impact, it is expected that Investigators and patients follow the protocol requirements as set forth.

# Visit schedule and procedures

- Visit 3, Visit 4, Visit 5, Visit 6, Visit 7, Visit 8, Visit 9, and Visit 10 windows extended to ±14 days as long as study drug supply is sufficient. If the extended window is used, any accompanying study drug interruption should not exceed 14 days.
- The screening period may be extended to a total of 12 weeks to account for potential delays in scheduling screening assessments. If the extended screening window is used, Investigators must ensure that the screening magnetic resonance imaging-proton density-fat fraction assessment is conducted within 8 weeks of randomization.
- If on-site visits cannot occur, assessments and safety follow-up may occur via telehealth, local community laboratories, and in-home visits by qualified nurses. The following visits may be replaced by telehealth or in-home visits: Visit 3, Visit 4, Visit 6, Visit 7, Visit 8, Visit 9, and Visit 10.
- Every effort should be made to utilize the central laboratory for study-specific laboratory assessments. If the patient must report to a local community laboratory for safety follow-up purposes, the following samples should be ordered from the local laboratory: biochemistry panel, hematology panel, coagulation, hemoglobin A1c, and low-density lipoprotein-cholesterol. Refer to Appendix B of the protocol to ensure all required analytes in a given laboratory panel are being collected by the local laboratory.

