Study drug dosing will begin at Visit 2 (Week 0, Day 0) and will continue daily for 52 weeks. During the 52-week treatment period, patients will return to the clinic for study visits every 1 to 3 months. The following assessments will occur at every study visit during the treatment period: adverse events, concomitant medications, body weight, vital signs, physical examinations, laboratory evaluations (hematology, biochemistry, coagulation, and lipid panels and urinalysis), and trough PK sampling. For a subset of patients (approximately 8 patients per group) at pre-identified sites, blood samples for analysis of additional PK parameters will also be collected predose and up to 24 hours postdose at Visit 2. In addition, hepatic imaging will be performed at Visit 5 (after 16 weeks of treatment) and Visit 9 (after 52 weeks of treatment).

Evaluation of liver inflammation and fibrosis biomarkers (Homeostatic Model Assessment for Insulin Resistance [HOMA-IR], hsCRP, Pro-C3, and ELF panel) will be performed at Visits 2, 5, and 9. Twelve-lead ECGs will be performed at Visits 2, 5, 7, and 9, and a liver biopsy will also be performed at Visit 9. Throughout the study, patients will be monitored for suspected drug-induced liver injury.

A Safety Follow-up Visit (Visit 10) will occur 14 days after the last dose of study drug to assess adverse events, concomitant medications, body weight, vital signs, physical examination findings, laboratory parameters, and 12-lead ECGs. Lipid parameters will be monitored throughout the follow-up period and will be managed by the Investigator.

Patients who discontinue early from the study for any reason prior to completion of the treatment period will be requested to return to the clinic for an Early Termination (ET) Visit as soon as possible after their last intake of study drug. Patients who discontinue early from the study for any reason after completion of the treatment period and before the Safety Follow-up Visit will be requested to return to the clinic for an ET Visit as soon as possible and no later than the planned Safety Follow-up Visit.

From screening through follow-up, the total study duration for each patient who completes the entire treatment period will be approximately 62 weeks. For a summary of procedures to be performed at each visit, refer to the Schedule of Procedures in Appendix A.

An external, independent DSMC will review all available unblinded preliminary safety and biomarker results per the DSMC Charter.

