## 5.5.2 Study Drug Preparation and Dispensing

Study drug will be dispensed as 300 mg capsules for oral administration at Visits 2 to 8 by blinded site personnel. Patients will receive enough study drug to last until the next study visit.

This study protocol includes contingency measures to manage disruptions due to COVID-19 control measures, including modifications to study drug dispensation specific to situations where COVID-19 is impacting study conduct. See Appendix G for details of COVID-19 contingency measures. In the absence of a COVID-19 impact, it is expected that Investigators and patients follow the protocol requirements as set forth.

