## 6.4 Safety Follow-up Visit (Visit 10, Week 54)

The Safety Follow-up Visit has a visit window of  $\pm 5$  days. The following procedures will be performed at the Safety Follow-up Visit (Visit 10, Week 54):

- Record concomitant medications.
- Measure body weight.
- Perform complete physical examination.
- Collect vital signs (blood pressure [3 readings], pulse rate, and body temperature) with the patient in the sitting position after 5 minutes of rest and before any blood draws.
- Collect fasting blood sample for the following:
  - o Hematology, biochemistry, coagulation, and lipid panels.
  - o Serum pregnancy test (only for women of childbearing potential).
- Collect urine sample for urinalysis.
- Perform 12-lead ECG after the patient has been resting in the supine position for at least 10 minutes.
- Assess adverse events.

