#### 8 SAFETY ASSESSMENTS

#### **8.1** Adverse Events

An adverse event is defined as any untoward medical occurrence in a clinical investigation patient administered a pharmaceutical product, which does not necessarily have a causal relationship with this treatment. An adverse event can therefore be any unfavorable and/or unintended sign (including an abnormal laboratory finding), symptom, or disease temporally associated with the use of an investigational medicinal product, whether or not related to the investigational medicinal product. All adverse events, including observed or volunteered problems, complaints, or symptoms, are to be recorded on the appropriate eCRF.

Adverse events, which include clinical laboratory test variables, will be monitored and documented from the time the patient signs the informed consent form (ICF) until Visit 10 (Week 54) or the ET Visit (if applicable). Patients should be instructed to report any adverse event that they experience to the Investigator, whether or not they think the event is due to study treatment. Investigators should make an assessment for adverse events at each visit and record the event on the appropriate adverse event eCRF.

Wherever possible, a specific disease or syndrome rather than individual associated signs and symptoms should be identified by the Investigator and recorded on the eCRF. However, if an observed or reported sign or symptom is not considered a component of a specific disease or syndrome by the Investigator, it should be recorded as a separate adverse event on the eCRF. Additionally, the condition that led to a medical or surgical procedure (eg, surgery, endoscopy, tooth extraction, or transfusion) should be recorded as an adverse event, not the procedure itself.

Any medical condition already present at screening should be recorded as medical history and not be reported as an adverse event unless the medical condition or signs or symptoms present at screening changes in severity, frequency, or seriousness at any time during the study. In this case, it should be reported as an adverse event.

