# 8.7 Clinical Laboratory Evaluations

Clinical safety laboratory parameters will be measured or calculated at all study visits (see Appendix A). Fasting hematology, biochemistry, coagulation, and lipid panels and urinalysis parameters will be evaluated at all study visits. Further analysis of urine sediment or urine microscopy will be performed if there are any abnormalities on any of the following 3 dipstick results: leukocyte esterase, blood, or nitrite. Although lipid parameters will be evaluated at every visit, lipoprotein particle size will be assessed only at baseline, Week 16, and at the end of treatment (Week 52/ET). Lipid parameters will be monitored throughout the follow-up period and any lipid-lowering treatment started during the study should be reviewed during the follow-up period and adjusted or discontinued in accordance with the 2018 AHA/ACC Guideline on the Management of Blood Cholesterol. See Appendix F for links to the full and abbreviated versions

of the 2018 AHA/ACC Guideline on the Management of Blood Cholesterol. See Appendix B for a complete list of laboratory analytes.

For women of childbearing potential, a serum hCG test will be performed at screening, Week 0, and at study exit (whether at the Safety Follow-up or ET Visit). Urine hCG testing will be performed at all other visits. If a urine hCG test is positive, pregnancy will be confirmed by a serum hCG test. Follicle-stimulating hormone level will be measured at screening to confirm postmenopausal state in women ≤55 years of age.

Samples will be collected for viral serology at screening to confirm patients are negative for hepatitis B virus, HCV (patients with a confirmed history of HCV infection can be included if HCV PCR is negative for at least the last 2 years), and HIV infection.

Blood sampling procedures, including information on blood volume, collection tubes, sample processing, storage, and shipping are provided in the Laboratory Manual. Where necessary, local laboratory testing will be acceptable to monitor events of suspected drug-induced liver injury.

Technical details on laboratory parameters (methods and commercial kit[s]) will be specified in the Laboratory Manual.

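### Minor: under the COVID-19 contingency, Visit 10 gets a two-sided ±14-day window, which leaves the safety follow-up visit with no minimum time off drug

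*Protocol*

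**What the plan says.** The protocol defines Visit 10 by its distance from dosing. Section 3.1 states: "A Safety Follow-up Visit (Visit 10) will occur 14 days after the last dose of study drug". SAP Section 2.2.1 likewise places it 2 weeks after the last dose. The ordinary tolerance is in Section 6.4, where "The Safety Follow-up Visit has a visit window of" is followed by ±5 days. Section 6 gives Visits 3 and 10 this narrower window and the other treatment-period visits ±7 days. The Schedule of Procedures (Appendix A) puts Visit 9 at Day 364 and Visit 10 at Day 378.

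Appendix G changes this where the pandemic disrupts the study. Its list of affected visits starts at Visit 3 and ends: "Visit 9, and Visit 10 windows extended to ±14 days as long as study drug supply is sufficient". A second condition limits any accompanying drug interruption to 14 days. The appendix is confined to disruption: "these mitigations are specific to situations where COVID-19 is impacting study conduct". It also lets Visit 10 be held by telehealth or at home.

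Three other rules depend on when Visit 10 takes place:

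- Section 8.1 ends adverse event recording at Visit 10 or the Early Termination (ET) Visit.
- Section 8.7 says that "any lipid-lowering treatment started during the study should be reviewed during the follow-up period and adjusted or discontinued".
- SAP Section 3.1.2 keeps the eCRF label for scheduled visits, and SAP Section 3.4.2.3 lists Week 54 among the liver-enzyme visits.

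**The concern.** A safety follow-up visit exists to observe patients after they stop the drug. A window that is symmetric and as wide as the planned interval allows that observation time to shrink to nothing. For Visits 3 to 9 an early or late visit only shifts a measurement made on treatment. For Visit 10 an early visit changes what is measured.

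Three things are at stake for patients who complete treatment. Collection of non-serious adverse events would stop with little or no off-drug time. The only scheduled follow-up laboratory and ECG values would in effect be on-drug values, yet would be summarised as Week 54. The lipid panel available for deciding whether to continue lipid-lowering treatment begun on study would not show lipids off drug. Patients who discontinue early are outside this point, because they leave at the ET Visit under Section 6.5.

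Elsewhere Appendix G adds a guard when it extends a window: longer screening is allowed only if the MRI-PDFF stays within 8 weeks of randomization. Visit 10 has no comparable guard.

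**Working it through.** **Inputs.** Planned interval from last dose to Visit 10: 14 days (Protocol Section 3.1). Ordinary Visit 10 window: ±5 days (Sections 6 and 6.4). Ordinary Visit 9 window: ±7 days (Sections 6 and 6.3). Appendix G window for both visits: ±14 days. Study days: 364 and 378 (Appendix A).

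**1. Reproduce the plan's own timing.** 52 × 7 = 364, and 364 + 14 = 378 = 54 × 7. This agrees with Day 378, Week 54.

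**2. Window counted from the last dose.** The permitted interval is 14 − w to 14 + w days.

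- Ordinary, w = 5: 14 − 5 = 9 to 14 + 5 = 19 days.
- Appendix G, w = 14: 14 − 14 = 0 to 14 + 14 = 28 days.

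**3. Window counted from fixed study days.** The smallest gap between Visits 9 and 10 is the earliest Visit 10 minus the latest Visit 9. The largest is the latest Visit 10 minus the earliest Visit 9.

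- Ordinary: (378 − 5) − (364 + 7) = 373 − 371 = 2 days, up to (378 + 5) − (364 − 7) = 383 − 357 = 26 days.
- Appendix G: (378 − 14) − (364 + 14) = 364 − 378 = −14 days, up to (378 + 14) − (364 − 14) = 392 − 350 = 42 days.

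A negative value means that the two windows overlap, so the dates alone no longer keep the visits apart.

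**4. Which anchor fits better.** Section 3.1 defines Visit 10 from the last dose. Section 5.5.3 lets dosing run up to 30 days past the projected Visit 9 date if the biopsy is late. With that date at Day 364, dosing could reach Day 364 + 30 = 394, after the latest fixed-day Visit 10 even under Appendix G (Day 392). The last-dose anchor is therefore the more workable reading, but the conclusion does not depend on it.

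**5. Search for a minimum elsewhere.** The two Appendix G conditions, sufficient drug supply and an interruption of at most 14 days, govern dosing. The appendix's provision for supplying or shipping extra drug also governs dosing. No other section of the protocol or SAP sets a minimum off-drug time for Visit 10.

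**6. Proposed window.** 14 − 5 = 9 to 14 + 14 = 28 days after the last dose.

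**The case against.** The strongest reply is that the harmful case is unlikely. Appendix G is written for delay, and the telehealth and in-home options remove much of the reason to bring Visit 10 forward. A Visit 10 on the last-dose day would largely repeat Visit 9, which already includes adverse events, laboratory tests, ECG, vital signs and a complete examination. No sensible site would plan it. This stands as an argument about frequency. It does not change what the rule permits, and a contingency rule is used when ordinary scheduling has failed.

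The second reply is that most consequences are already covered. SAEs are reported to 30 days after the last dose whatever the date of Visit 10 (Section 8.3). Clinically significant laboratory values are followed (Section 8.1), and patients stopped under the liver criteria are followed to resolution (Appendix E). Section 8.7 asks for lipid review during follow-up without tying it to a single Visit 10 value. All of this stands, and it leaves non-serious adverse events and one set of off-drug safety values.

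The third concerns timing. The SAP, dated 14 February 2023, describes the study in the past tense, so amending the protocol text may change little. That limits the benefit of the amendment, but the gap in the rule remains.

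Two stronger readings should be resisted. A reader might infer that the ordinary protocol guarantees 9 days off drug; that holds only if the window is counted from the last dose, since fixed study days allow a 2-day gap between Visits 9 and 10. A reader might also infer that the supply condition is empty because "Study drug will be dispensed as 300 mg capsules for oral administration at Visits 2 to 8". That section goes on to defer to Appendix G, which allows extra supply and direct shipment. The sound argument is narrower: none of these supply rules sets a minimum time off drug.

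**Conclusion.** The point holds as a minor one. Under Appendix G the permitted off-drug interval goes from 9–19 to 0–28 days counted from the last dose. Counted from fixed study days, the gap between Visits 9 and 10 goes from 2–26 days to −14 to 42 days. Either way the lower limit is lost and nothing else in the documents restores it.

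The documents do not support a larger claim about impact. A reader might note that days 0 to 8 are 9 of the 29 days permitted from the last dose and treat that as a risk; it is a count of calendar days, not a probability or a share of patients. The documents do not say how many patients would have an early Visit 10 because of COVID-19; probably few would.

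Nor do they support a claim that efficacy conclusions are at risk. The primary endpoint comes from the liver biopsy and is unaffected. Values labelled Week 54 can enter the SAP's liver-enzyme model, but the protocol's comparison is at Week 52 (Section 9.2.1.4), and SAP Section 3.1.5 treats p-values for the other secondary endpoints as nominal.

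**What to change.** Remove Visit 10 from the common ±14-day list in Appendix G and add: *The Visit 10 window is −5/+14 days, counted from 14 days after the actual last dose of study drug (9 to 28 days after the last dose).*

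This fixes the anchor as well as the minimum. Do not tie Visit 10 to Visit 9 or to the biopsy, because SAP Section 3.2.3 accepts an end-of-treatment biopsy up to 90 days from the last dose or Week 52 visit. If a biopsy falls more than 28 days after the last dose, Visit 10 will precede it, as it would under the present 0–28 day reading.

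The cost is one sentence, with no extra visits or procedures. Sites lose the ability to bring Visit 10 forward by more than 5 days; the 14-day late side and the telehealth or in-home option remain. If the visits have already taken place, the days from last dose to Visit 10 could be listed from dates already collected, so that readers can see whether any early visits occurred.

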# 8.4 Pregnancy Reporting

If a patient becomes pregnant during the study or within the safety follow-up period (ie, prior to the Safety Follow-up Visit), the Investigator is to stop dosing with study drug(s) immediately, and the patient should be withdrawn from the study. Early termination procedures should be implemented at that time.

A pregnancy is not considered to be an adverse event or SAE; however, it must be reported to Medpace Clinical Safety within 24 hours of knowledge of the event. Medpace Clinical Safety will then provide the Investigator/site the Exposure In Utero (EIU) form for completion. The Investigator/site must complete the EIU form and fax/email it back to Medpace Clinical Safety.

If the female partner of a male patient becomes pregnant while the patient is receiving study drug or within the safety follow-up period, the Investigator should notify Medpace Clinical Safety as described above.

The pregnancy should be followed until the outcome of the pregnancy, whenever possible. Once the outcome of the pregnancy is known, the EIU form should be completed and faxed/emailed to Medpace Clinical Safety. If the outcome of the pregnancy meets the criteria for immediate classification as an SAE (ie, postpartum complication, spontaneous abortion, stillbirth, neonatal death, or congenital anomaly), the Investigator should follow the procedures for reporting an SAE.

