# Study drug dispensation

- Patients may be supplied with additional study drug during a visit if there is a concern that the
  patient may not be able to report to the site as scheduled for the next required visit. This will
  ensure that patients have enough study drug to accommodate extended visit windows or
  telehealth visits.
- In some circumstances, it may be necessary to ship study drug directly to the patient. Shipping will be performed by a qualified professional courier who is contracted by the Sponsor or Contract Research Organization. The courier will be responsible for providing packing materials and cold chain monitoring to complete the shipment. Patients must consent to providing personal data to the courier to complete the shipment. Refer to the Pharmacy Manual for additional details.

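### Appendix G's reduced local-laboratory list omits the pregnancy test that Section 8.7 requires at every visit, and no other remote route is assigned it

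*Protocol*

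**What the plan says.** **Ordinary schedule.** For women of childbearing potential, Protocol Section 8.7 states that "a serum hCG test will be performed at screening, Week 0, and at study exit", and then that "Urine hCG testing will be performed at all other visits". Footnote l of the Appendix A schedule and the Endocrinology footnote in Appendix B repeat this. The visit lists in Sections 6.2 to 6.5 include a pregnancy test at every visit.

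**COVID-19 contingency.** Where on-site visits cannot occur, Appendix G says that "assessments and safety follow-up may occur via telehealth, local community laboratories, and in-home visits by qualified nurses". The visits that "may be replaced by telehealth or in-home visits: Visit 3, Visit 4, Visit 6, Visit 7, Visit 8, Visit 9, and Visit 10" are all those after Visit 2 except Visit 5. The central laboratory is preferred. The fallback is introduced by "If the patient must report to a local community laboratory for safety follow-up purposes", and for that case "the following samples should be ordered from the local laboratory: biochemistry panel, hematology panel, coagulation, hemoglobin A1c, and low-density lipoprotein-cholesterol". Appendix G then points to Appendix B for the analytes within each listed panel.

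**Drug supply.** Appendix G allows extra drug to be handed out ahead of a visit that may be missed, and adds: "In some circumstances, it may be necessary to ship study drug directly to the patient". Pregnancy testing is not mentioned anywhere in Appendix G.

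**Consequence of pregnancy.** Under Section 8.4, if a patient becomes pregnant, "the Investigator is to stop dosing with study drug(s) immediately" and she is withdrawn.

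**The concern.** In the ordinary schedule each visit at which drug is dispensed (Visits 2 to 8) also includes a pregnancy test, so supply and testing happen together. Appendix G separates them. Drug can reach the patient without a site visit, and the one place where Appendix G says which samples to take does not name hCG.

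The stake is patient safety. The Section 8.4 stop rule largely depends on pregnancy being detected, and scheduled testing is the protocol's planned means of detection. A missed test lengthens the time for which a woman could be dosed before a pregnancy is found. No efficacy estimate, error rate or sample size is affected.

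**Working it through.** The plan states no testing interval that could be reproduced, so the check has two parts: a comparison of the passages, and the intervals that follow from the visit schedule.

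**1. Is hCG on the Appendix G list by another route?**

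- The list has five items: biochemistry, hematology, coagulation, hemoglobin A1c and LDL-C.
- The pointer to Appendix B concerns analytes inside a listed panel. In Appendix B, hCG stands under Endocrinology, which is not one of the five.
- The list is visibly a reduced set. It takes LDL-C in place of the full lipid panel and has no urinalysis. A site has reason to read it as the sample set for that situation.
- Telehealth and in-home nurse visits have no sample list of their own, and no sentence assigns the pregnancy test to either.

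The test is therefore required by Section 8.7 and left unassigned by Appendix G.

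**2. How long could the gap be?**

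Inputs, from Appendix A: Visits 2 to 10 fall at Weeks 0, 4, 10, 16, 24, 32, 40, 52 and 54. From Appendix G: Visits 3, 4, 6, 7, 8, 9 and 10 can be replaced, so from Week 0 on only Visits 2 and 5 cannot. From Section 3.1: planned dosing ends at Week 52.

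Interval = week of the later test − week of the earlier test.

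| Case | Calculation | Weeks |
|---|---|---|
| Longest ordinary interval (Visit 8 to 9) | 52 − 40 | 12 |
| Visits 3 and 4 untested | 16 − 0 | 16 |
| Visits 6, 7 and 8 untested, to planned end of dosing | 52 − 16 | 36 |
| Visits 6 to 9 untested, to Visit 10 | 54 − 16 | 38, of which 2 are after the last planned dose |

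The on-drug maxima are thus 16 weeks before Visit 5 and 36 weeks after it. They are two separate stretches. The 36-week case does not need a remote Visit 9: a test at Week 52 closes the interval just as dosing is due to end.

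Sensitivity to timing, using Appendix G's ±14-day windows and days 112 and 364 for Visits 5 and 9:

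- Visit 2 to 5: (112 ± 14)/7 = 14 to 18 weeks.
- Visit 5 to 9: from (364 − 14 − 126)/7 = 32 to (364 + 14 − 98)/7 = 40 weeks.
- If the Visit 9 biopsy is delayed and dosing continues for the 30 days allowed in Section 5.5.3: (364 + 30 − 112)/7 = 40.3 weeks from a nominal Visit 5 to the last dose.

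**3. What does a single missed test do?**

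| Only this visit untested | Interval | Weeks |
|---|---|---|
| Visit 3 | 10 − 0 | 10 |
| Visit 4 | 16 − 4 | 12 |
| Visit 6 | 32 − 16 | 16 |
| Visit 7 | 40 − 24 | 16 |
| Visit 8 | 52 − 32 | 20 |

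One missed test at Visit 6, 7 or 8 already exceeds the ordinary 12-week maximum. One at Visit 3 or 4 does not.

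**The case against.** The strongest reply is that nothing in Appendix G cancels Section 8.7. The list says which samples should be ordered, not that only these may be. Appendix G changes where assessments happen, and its silence on other items, such as PK samples at remote visits, does not abolish them. The test due at Visits 3 to 9 is on urine, while the list names only blood tests. Operational detail may also sit in the Pharmacy and Laboratory Manuals, which are not part of these documents.

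This stands in part. It rules out the reading that the protocol permits dosing without tests: the requirement is left unassigned, not withdrawn. It does not remove the conflict. Section 6 and Appendix A present Appendix G as changing visit timing and procedures during disruption, and Appendix G expects the protocol as written to be followed when COVID-19 has no impact. A site can reasonably take the shorter list as the operative one.

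A reader might infer more, in four ways that the documents do not support:

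- **That the list governs every remote visit.** It governs the local-laboratory route only. An in-home nurse could do the test, and the central laboratory is preferred.
- **That a woman could be on drug untested for anything from 16 to 38 weeks.** These figures are not a range, and 38 weeks runs to Visit 10, two weeks after planned dosing ends. It also needs a remote Visit 9, although that visit carries the biopsy and MRI.
- **That the stop rule could not act.** Section 8.4 is triggered by pregnancy however it becomes known. Serum tests at screening and Week 0, and dual contraception until 90 days after the last dose, also remain in force.
- **That drug may be dispensed only after a negative result.** The visit lists in Section 6.3 set testing and dispensing side by side but never make one wait for the other.

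**Conclusion.** The concern holds as a conflict between Appendix G and Section 8.7 with Appendices A and B. The pregnancy test is required at every visit, is absent from the reduced local-laboratory list, and is assigned to no remote route.

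The two nominal worst cases on drug are 4/3 and 3 times the longest ordinary interval (16/12 and 36/12). They assume COVID-19 disruption, a woman of childbearing potential, every replaceable visit inside the stretch held remotely, and a site that follows the list each time. The documents give no frequency for this combination. SAP Section 3.3.1 will count virtual visits, but that does not show whether a test was done. The expected effect is therefore delayed detection in some patients, of unknown number. The correction is worth making because it is small and bears on patient safety.

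**What to change.** Reconcile the two parts of Appendix G (visit schedule and procedures; study drug dispensation) with Section 8.7, Appendix A including footnote l, and the Endocrinology entry of Appendix B. After the change, the sample list and the text on telehealth and in-home visits should account for the hCG test that the protocol already requires at each visit. How the test is done remotely, and whether it is tied to shipment of drug, are for the sponsor to decide.

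The text change is about one line in the list and a sentence on the remote routes, made as a protocol amendment with IRB approval under Section 12.1. Running costs depend on the method chosen. The SAP needs no change.
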